Project Title:

LIDOCAINE IN THE TREATMENT OF POST-OPERATIVE PAIN
MANAGEMENT FROM A DONOR SITE AFTER SPLIT THICKNES SKIN GRAFT
HARVESTING FOLLOWING BURN INJURY OR WOUND TREATMENTS

NCT #:

NCT02229578

Document date:

December 08, 2016

Protocol

1. Project Title:

LIDOCAINE IN THE TREATMENT OF POST-OPERATIVE PAIN MANAGEMENT FROM A DONOR SITE AFTER SPLIT THICKNESS SKIN GRAFT HARVESTING FOLLOWING BURN INJURY OR WOUND TREATMENTS

2. Investigator(s): **[name]**

[name]

[name]

[name], ARNP

[name]

3. Abstract:

Burn pain is known to be one the most severe forms of acute pain often requiring large amounts of narcotics in addition to other adjuvants. Wounds can also cause a great deal of pain in this population. Topical lidocaine is effective for controlling pain in various settings including dressing changes of burns. The aim of this study is to demonstrate the effectiveness of topical lidocaine in decreasing pain scores and narcotic requirements when applied to donor graft sites while at the same time not interfering with the standard of care TheraBond dressing. During this study we will be monitoring for evidence of delayed wound healing, and surgical site infection.

4. Background:

Pain from burns is a severe form of acute pain that requires aggressive use of opioids.¹ Even with the implementation of multiple modalities for analgesia, pain from skin debridements and grafting procedures remains a challenge to control.^{2,3} Local anesthetics have been used for pain relief in burn patients previously as a topical gel or IV infusion and have been found to significantly reduce medication consumption, without apparent adverse effects on wound healing.^{2,4,5} Lidocaine actually has potent anti-inflammatory effects which could be advantageous on wounds.¹ In addition, topical application of lidocaine to wounds result in different degrees of systemic absorption. High concentrations of lidocaine have potential for central nervous system (seizures ($>5\text{mg/L}$)) and cardiovascular toxicity (arrhythmias ($>9\text{mg/L}$)).⁴ Plasma concentration of lidocaine depend upon drug dose, rate of absorption, patient weight, physical status and thickness of skin harvested.⁶ A prior study where up to 6.7mg/kg of 2% lidocaine with epinephrine was sprayed on donor

graft sites found that systemic lidocaine levels were far below toxic levels at their peak (average level of 1.4, with maximum level at 2.2). In this study the levels peaked between 30 and 60 minutes and systemic levels of lidocaine were detectable 6 hours following application of the solution.² Studies have demonstrated the beneficial effects of systemic lidocaine administered via IV infusions in reducing perioperative pain scores.^{7, 8} Topical lidocaine is effective as a topical anesthetic in multiple clinical trials however only two studies to date has shown that topical lidocaine applied to skin-harvest sites produces an analgesic effect, reduces narcotic requirements while not affecting wound healing or causing toxic blood concentrations. In both these studies systemic intravenous lidocaine levels were monitored and were found to be significantly below toxic limits.^{2,9} The use of topical lidocaine on donor sites is still not widely used, partly for fear the lidocaine will interfere with wound healing and/or dressing adherence. No study to date has demonstrated lidocaine solution to be effective on burn sites when used in conjunction with TheraBond silver foam dressing. TheraBond is an absorbent, atraumatic dressing coated with ionic silver that is routinely used on donor sites at our institution. This study will also offer additional supporting evidence that topical lidocaine is effective in post-operative pain management of donor skin sites and should be more widely utilized. In addition, this study will serve as a stepping stone for analyzing different local anesthetic solutions in the future and the potential for reapplication to surgical sites.

5. Specific Aims:

The purpose of this study is to offer the medical community data on a simple and relatively cheap adjuvant that can be utilized to help reduce the amount of post-operative pain and narcotic requirement in burn and wound patients requiring skin grafts.

6. Research Plan:

Study Design

- a) Randomized Controlled Double-Blind Study
- b) Burn and wound patients undergoing general anesthesia for split thickness skin graft with a 1-15% TBSA donor site who will be treated at UF Health Shands Hospital
- c) Consent will be obtained from non-intubated patients willing to participate in the study that are admitted to the Burn Service for treatment of their burn or wound. All patients will undergo general anesthesia. Standard induction will be performed with Fentanyl and Propofol. Maintenance will primarily be with the volatile agent sevoflurane. Acetaminophen 1g IV and Ketorolac 30mg IV will be administered for baseline pain control intraoperative within the last 30 minutes prior to extubation. Fentanyl, Hydromorphone or Morphine will be

titrated in at end of the case as part of standard management. Hydromorphone, as needed (PRN), orders will be written for pain control in the recovery room as well as one time dose of Oxycodone 5-15mg PO. If patient requires more than 2mg of Hydromorphone then subsequent pain will be treated with Ketamine IV (10mg every 15 minutes up to 50mg total) and 1-2mg of IV midazolam. If pain is still not adequately controlled patient will be treated with an additional 2mg of Hydromorphone IV and Hydromorphone PCA will be initiated. Once discharged from the PACU to the surgical floor the patient will have PRN Oxycodone PO every 4 hours and/or Hydromorphone PO every 4 hours in addition to PRN Hydromorphone 0.2-0.5mg available. If pain control is still not adequate patient will be started on Hydromorphone PCA. The amount of hydromorphone required in PACU and in the first 24 hours following surgery will be compared between the two groups as well as self-reported donor site and overall pain according to the Verbal Numerical Rating Scale (VNRS) obtained from the patient by Research staff and by the hospital staff per standard of care.

- d) Lidocaine 2% with Epinephrine 10 μ g/mL will be placed on the donor site immediately following harvesting until hemostasis has been obtained per the surgeon. The total of up to 7mg/kg, as recommended by leading anesthesia textbooks, of lidocaine solution will also be sprayed onto the patient's donor site based on patient's ideal weight (BMI 25 or actual patient's weight if BMI <25).¹⁰
- e) 50 patients split into two (study & control) groups.
 - a. Group A patients will have sterile 2% lidocaine with Epinephrine 10 μ g/mL (Solution A1) soaked in surgical grade cotton applied to the donor site immediately after donor harvest until hemostasis is obtained according to the surgeon. If additional hemostasis is deemed necessary by the surgeon following use of 20cc (1 vial) of this Solution A1 then additional Epinephrine 10 μ g/mL will be used as per standard burn protocol. Following hemostasis, patients will have a sterile, nonpyrogenic solution of lidocaine 2% in isotonic saline (Solution A2) sprayed on the donor site of the grafted skin prior to emergence from general anesthesia. A maximum of 7mg/kg of lidocaine solution will be available for spraying. The site will then be covered with TheraBond dressing as per standard burn care used at our institution.
 - b. Group B (control group) patients will have sterile Epinephrine 10 μ g/mL solution (Solution B1) soaked in surgical grade cotton applied to the donor site immediately after donor harvest. A 20cc aliquot will be prepared in such a way as to be indistinguishable from Solution A1 by the OR team. If additional hemostasis is deemed necessary by the surgeon following use of 20cc (1 vial) of this Solution B1 then additional Epinephrine 10 μ g/mL will be used as per standard burn protocol. Following hemostasis, patients will have a control (placebo) sterile, nonpyrogenic solution of isotonic saline (Solution B2) sprayed over the donor site. The site will then be covered with TheraBond dressing as per standard burn care used at our institution.

- f) Assessment of the donor sites using the VNRS pain scores will be compared between groups in addition to the amount of narcotic pain medication required by these two groups. The amount of narcotic utilized will be analyzed per ideal body weight, per actual body weight in addition to donor site area.
- g) Lidocaine levels will be drawn at sixty minutes and six hours from application of study solution. These levels will be analyzed on a per patient and per graft size area basis to trend for systemic levels.
- h) Any adverse event occurring with the patient will be analyzed on a case-by-case basis. Wound infection rates of the donor sites at post op day 14-21 +/- 5 days will be compared between the two groups. Any adverse event deemed serious by the Principal Investigator will be submitted to the Institutional Review Board per institution policy.
- i) All care offered during this treatment, including intraoperative medication use, surgical application of dressing and post-operative wound assessments are currently part of standard burn care at our institution. The only new variable we are analyzing is the addition of the lidocaine/placebo solution to the donor site intraoperatively.

Intraoperatively a TheraBond dressing will be applied to the donor site that later "falls off" once the site has healed. Outer dressings of gauze, Bioguard and Acewraps will also be applied, covering the Therabond and will be changed daily per standard of care. Wound healing of the donor site will be evaluated visually by the burn research team and the time in days of TheraBond dressing removal will be analyzed. In addition, photographs of the donor sites will be obtained intraoperatively and at the time the TheraBond comes off.

Study Procedures

- a. Subject selection procedures
 - i. Inclusion criteria: Adult patients who have suffered second to third degree burns or have a wound requiring a single split thickness skin graft surgery. Donor sites will be estimated to be between 1-15% TBSA. Patients who have history of major renal and/or liver dysfunction, history of seizures or major neurologic deficiencies, allergy to local anesthetics, reported allergy to hydromorphone, pregnancy, or currently have other injuries that significantly contribute to pain (i.e. multi-trauma patients) will be excluded from the study.
 - ii. Consent will be obtained from all patients. The risk and benefit topical lidocaine will be explained to each patient and a consent for this study will be obtained. Burn and wound patients require high doses during wound related procedures and for post-operative pain control. At other times their background pain is easily controlled by much lower doses of narcotics; they remain alert and are capable of making complex decisions.

- iii. If a patient is found to be in pain out of proportion to injury at hand and demonstrate an inability to focus on the consent they will not be considered for enrollment in the study.
- b. Randomization procedures: Numerical randomization will be created using a computer generated numbers. Randomization envelopes will be created by research staff and maintained by the Investigational Drug Pharmacy. The Burn Study Team will alert the Investigational Drug Pharmacy to randomize each patient. The Investigational Drug Pharmacy will dispense the appropriate blinded solution for treatment. The Investigational Drug Pharmacy will dispense Lidocaine with Epinephrine or Epinephrine alone in blinded fashion for the donor site soaks. A 20cc bottle of Lidocaine with Epinephrine or Epinephrine alone will be emptied into a sterile unlabeled container prior to application of sprayed study treatment. The surgeon and OR team will remain blinded for this portion of the study. If additional hemostasis is required beyond the first study soak treatment; then the standard of care epinephrine soak will be utilized. The Investigational Drug Pharmacy will also dispense the randomized spray study treatment in an assembled applicator (LMA MADgic™) purchased for this project only. No unblinding identifiers will be on either applicators. The investigator will be blinded to all groups. Study Intervention:
 - i. Group A (Lidocaine Treatment Group): Graft site hemostasis will be obtained with 2% lidocaine and epinephrine 10 μ g/mL solution in normal saline soaked in surgical grade cotton gauze and placed over donor site for time determined by surgeon. Following hemostasis, 7mg/kg of 2% Lidocaine solution will then be sprayed on patient's donor site while under general anesthesia by burn surgeon in a sterile fashion. Upon emergence and transfer to PACU patient will be asked to rate his/her pain according to the VNRS for both donor site and overall pain. The amount of narcotics required in PACU and first 24 hours on floor will be documented. Rate of increase of narcotic requirement within the first 24 hours will also be analyzed. VNRS scores will be obtained immediately post operatively on arrival to PACU and in 24 hours.
 - ii. Group B(Placebo Group): Graft site hemostasis will be obtained with a epinephrine 10 μ g/mL solution in normal saline soaked in surgical grade cotton gauze and placed over donor site for time determined by surgeon. Following hemostasis a control solution will be sprayed on patient's donor site while under general anesthesia by burn surgeon in a sterile fashion. Upon emergence and transfer to PACU patient will be asked to rate his/her pain according to the VNRS for both donor site and overall pain. The amount of narcotics required in PACU and first 24 hours on floor will be documented. Rate of increase of narcotic requirement within the first 24 hours will also be

analyzed. VNRS scores will be obtained immediately post operatively on arrival to PACU, 6 hours post treatment during blood draw and in 24 hours for both donor site and overall pain.

Study Table of Events

Study Assessments	Baseline	Surgical Procedure	0-24 hours post op	24-48 hours post op	Follow up (14-21 days)*
Informed Consent	X				
Inclusion/Exclusion	X				
Demographic Data	X				
Medical History	X				
Physical Exam	X				
Randomization		X			
Treatment		X			
OR Data Collection		X			
VNRS Pain Assessment			X**	X**	
Self-Reported Pain Assessment			X	X	
Wound Healing Assessment					X
Photographs		X			X

Narcotic Medication Data Collection		X	X	X	
Adverse/SAE Assessment	X	X	X	X	X
Lidocaine Level			X***		

* (+/- 5 days)

**Performed at 30 minutes after extubation, 2 hours, 6 hours and 24 hours post-op for both donor site and overall pain

***Performed at 60(+/-30 minutes) minutes and 6 hours (+/-60 minutes) post op

Safety Monitoring Plan

- a. The likelihood of adverse events in this study is very small. Lidocaine spray doses will be calculated (7mg/kg based on ideal body weight) to ensure patient is receiving safe doses. A safety analysis performed on our first 15 patients proved safety. All lidocaine levels obtained demonstrated levels significantly lower than potentially toxic dosing. We believe there could be improved pain control if more appropriate (higher) lidocaine doses are utilized. The method suggested for hemostasis with lidocaine and epinephrine is standard of care at some institutions including our own. It is regularly used by the ENT service. In addition, one of the surgeons in our study has used this method in the past.
- b. Patients will be monitored with pulse oximetry overnight per standard of care.
- c. All patients enrolled in the study will have risks and benefits thoroughly explained to them.
- d. Any adverse events will be well documented and thoroughly investigated. Seriousness of event will be assessed by the Principal Investigator. All events deemed serious will be submitted to the University of Florida Institutional Review Board in accordance with institutional policy.
- e. Dressing site will be evaluated daily per standard of care by the burn team until hospital discharge.
- f. After 10 additional evaluable patients, have been enrolled a second safety analysis will be performed; all investigators will be involved in data interpretation.

Analysis Plan

An independent groups t-test (Student's t-test) will be performed to compare the mean rating between the difference of the two reported pain scale ratings. Each patient will be used as his/her own control by comparing the amount of narcotics utilized prior to surgery. An alpha level of 0.05 and power of 0.8 will be used to address the difference in the two groups. Given the desired alpha the sample size was estimated by pre-determined tables for certain values, by Mead's resource equation. With an effect size (Cohen's d) of 0.8 it is estimated that 25 patients in each

group will be needed in order to show statistical significance. An interim analysis will be conducted at 10 patients in each group and significance will be analyzed.

The amount of hydromorphone utilized in the PACU immediately post op and within the first 24 hours will be compared between the two groups and trended within the same group. Once again, an independent groups t-test will be performed to compare the mean quantity of hydromorphone required between the two groups. An alpha level of 0.05 and power of 0.8 will be used to address the difference in the two groups.

7. Possible Discomforts and Risks:

The patient's regular medical care will not change because they are enrolled in this study.

Possible risks to you may include:

- The risks from skin grafting and donor site include those associated with any surgical procedure that involves general anesthesia. These include reactions to the anesthesia, medications, nausea, pain, problems breathing, excessive bleeding, and infection.
- If a wound becomes infected, it may result in the need for further surgical treatment. Surgical treatment could include debridement of the wounded area (surgical removal of dead or infected tissue of the wound), and/or regrafting. Because your doctor looks at the wounds very closely, he/she will try to take care of any complications as fast as they can. The treatment of side effects and complications will be the same that would be expected for the treatment of side effects and complications for any skin grafting and donor site procedure performed at the hospital.
- Side effects of Lidocaine include: Nausea, drowsiness, mental/mood changes, ringing in the ears, dizziness, vision changes, tremors, numbness, headache and backache. Serious adverse effects could include fever, unusually fast and slow pulse, trouble breathing, seizures and chest pain. An allergic reaction to Lidocaine could include: rash, itching, swelling, dizziness, and trouble breathing.
- Side effects of drawing blood from a vein include discomfort at the site of puncture; possible bruising and swelling around the puncture site; rarely an infection; and, uncommonly, faintness from the procedure. Blood drawn each time will be approximately 5 teaspoons. The total amount drawn during the study will be approximately 10 teaspoons.

8. Possible Benefits:

Patients randomized to the treatment group may have increased satisfaction, increased pain control, decreased narcotic usage, and a decrease in chronic pain.

9. Conflict of Interest:

There is no conflict of interest involved with this study beyond professional benefit from academic publication or presentation of results.

Literature Cited

6. Derek JD. Local and regional anaesthesia. *Baillieres Clin Anaesthesiol* 1987;1:715–28.

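### Narcotic use is to be analysed raw and scaled to two body weights and donor-site area, with no version ranked and none adjusted for covariates

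*Combined protocol and SAP*

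**What the plan says.** Section 6, Study Design f), says that narcotic use will be "analyzed per ideal body weight, per actual body weight in addition to donor site area". No order of priority is given, and no test is named for these scaled quantities.

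The Analysis Plan does not mention scaling. On the time windows it says: "The amount of hydromorphone utilized in the PACU immediately post op and within the first 24 hours will be compared". On the method: "an independent groups t-test will be performed to compare the mean quantity of hydromorphone required between the two groups". No covariate enters that test.

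Pre-surgery use appears only as an own-control comparison: "Each patient will be used as his/her own control by comparing the amount of narcotics utilized prior to surgery". How it enters the between-group comparison is not stated.

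Eligibility allows a "split thickness skin graft with a 1-15% TBSA donor site". Section 6 d) takes ideal weight as the weight at BMI 25, or actual weight if BMI is lower, so the two weights coincide below BMI 25. Height, weight and donor-site dimensions in cm² are on the case report forms.

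**The concern.** There are two problems.

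**Ranking.** Section 6 f) and the Analysis Plan together give four versions of the narcotic outcome: raw, per ideal kg, per actual kg and per area. With two windows, that allows up to 4 × 2 = 8 comparisons. If they disagree, the plan does not say which one answers the question, although reducing narcotic requirement is a stated aim.

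**Efficiency.** A ratio removes variation due to its divisor only when the outcome is nearly proportional to that divisor. Several features of the plan make this doubtful for donor area. Patients use narcotics before any donor site exists, donor-site and overall pain are scored separately, and the burn or wound hurts too. When part of the need is unrelated to donor area, dividing by area adds noise, and patients with very small donor sites dominate the mean. Entering area and weight as covariates uses the same information without assuming proportionality.

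**Working it through.** **1. The plan's own figure.** The inputs are d = 0.8, alpha 0.05 (taken as two-sided) and power 0.80, all from the Analysis Plan. Then n per group = 2 × (1.960 + 0.842)² / 0.8² = 24.5, so 25, which matches the plan. The noncentral-t solution is 25.5, so 26. Power at 25 per group is 0.807 (normal) or 0.791 (t). The d = 0.8 stands with the pain-rating test. The narcotic paragraph repeats alpha and power but gives no effect size or SD of its own.

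**2. Why the ratio is fragile.** Write use as Y = a + bA + e, with A the donor area. Then Y/A = b + a/A + e/A. If a = 0, dividing removes the area effect. If a > 0, the term a/A varies 15-fold between A = 1 and A = 15, and the variance of e/A varies 15² = 225-fold when e has constant variance. For example, a use of 10 units unrelated to area becomes 10 at 1% and 10/15 = 0.67 at 15%.

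**3. Power by simulation.** The documents give no narcotic SD, no correlation with area and no area distribution, so these are assumed: 25 per group, true d = 0.8 on the total, CV 50%, area uniform on 1-15%, correlation of total with area 0 to 0.5.

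| Analysis | Power |
|---|---|
| Per donor area | 0.29-0.59 |
| Raw total | 0.78 |
| Total adjusted for area and weight | 0.77-0.87 |
| Per kg (ideal or actual) | about 0.72-0.77 |

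A second set used mean 10 and SD 4, with area and actual weight explaining stated shares of variance (R²), and area uniform:

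| R² area + weight | Raw | Per ideal kg | Per actual kg | Per area | Adjusted |
|---|---|---|---|---|---|
| 0 + 0 | 0.78 | 0.73 | 0.68 | 0.23 | 0.76 |
| 0.10 + 0.05 | 0.79 | 0.78 | 0.76 | 0.35 | 0.84 |
| 0.25 + 0.10 | 0.80 | 0.81 | 0.80 | 0.49 | 0.92 |
| 0.40 + 0.10 | 0.78 | 0.80 | 0.80 | 0.62 | 0.97 |

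With log-normal area (median 4%), the per-area column becomes 0.35, 0.49, 0.61 and 0.72.

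**4. Gain from adjustment by formula.** Power = Φ(0.8/√(1 − R²) × √(25/2) − 1.96). This gives 0.81 at R² = 0, 0.85 at 0.10, 0.90 at 0.25 and 0.95 at 0.40.

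**5. The favourable case for the ratio.** Assume a 28% multiplicative reduction, log-normal error with SD 0.35 and uniform area. Vary the share of control need that does not come from donor area:

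| Share from elsewhere | 0% | 10% | 20% | 30% | 50% | 70% |
|---|---|---|---|---|---|---|
| Per area | 0.89 | 0.83 | 0.75 | 0.62 | 0.42 | 0.29 |
| Linear model, adjusted | 0.80 | 0.82 | 0.83 | 0.84 | 0.86 | 0.86 |

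A model of log total on log area gives 0.88-0.91 throughout. Under exact proportionality the raw total has only 0.40.

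**6. Disagreement and false positives.** This applies if all three scaled versions were tested. In the second set (both area distributions), they split between significant and not in 38-59% of trials with a true effect. With no effect, including the proportional setting, at least one reaches p < 0.05 in about 0.08-0.12 of trials. Adding the raw test makes it 0.09-0.13.

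**The case against.** The strongest reply is that the Analysis Plan already tests the raw total. A reader might infer from f) that ratios replace the total and are themselves compared by t-test. The documents do not support that: the only narcotic t-test is on the unscaled quantity, and f) names no test. This stands. The ratios are additional analyses without a stated role, and the false-positive figures apply only if they are tested and one is selected.

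Second, f) does not write per before donor area, whereas g) does use that wording for lidocaine levels and graft size. Division is the natural reading but not the only one, and the per-area power figures depend on it.

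Third, a reader might infer that dividing by area always loses power. It does not. At a correlation of 0.7 the ratio reaches 0.84-0.89, above the raw total's roughly 0.78, and under exact proportionality it also beats the linear adjusted model. That second advantage is gone once about 10-20% of need comes from elsewhere, and log-scale adjustment matches the ratio even at 0%.

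Fourth, the weight ratios are not a serious power problem. The worst simulated loss against the raw total is about 11 points (0.675 against 0.782, per actual kg with use unrelated to weight). It disappears once use relates modestly to weight and area. The two weight versions also overlap heavily, so treating the three scalings as independent chances (1 − 0.95³ = 0.14) overstates the inflation.

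**Conclusion.** The point holds as one of ranking and efficiency. The plan carries an unadjusted raw test and several scaled versions, does not say which counts, and makes no use of donor area or weight as covariates although both are recorded.

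Adjustment costs about one or two points of power if the covariates explain nothing, and gains roughly 9 points at a correlation of 0.5 (0.78 to 0.87). The per-area ratio, if that is what is meant, falls 19 to 49 points below the raw total across correlations 0 to 0.5 (0.78 − 0.59 and 0.78 − 0.29).

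These sizes rest on an assumed CV, area distribution and correlation, and on applying the pain-score d = 0.8 to narcotic use. The documents cannot settle how close to proportional need is. The case for adjustment does not depend on settling it, because the adjusted model, on a log scale if needed, performs well in both situations.

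**What to change.** In the Analysis Plan, name one main narcotic analysis. The outcome is total use in one stated window, for example the first 24 hours, log-transformed if skewed. State whether this is hydromorphone alone or all narcotics, since f) and the Analysis Plan use different terms. Fit a linear model with arm, donor-site area in cm² (summed over sites, as the form has one page per site), one stated body weight and, where available, pre-surgery narcotic use.

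State that the other window and the per-weight and per-area versions are descriptive or sensitivity results and not tests of efficacy. Reword f) so that the treatment of donor area is explicit and agrees with the Analysis Plan.

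The cost is a few sentences and two or three degrees of freedom: from 50 − 2 = 48 residual to 46 or 45. Area and weight are already collected. Pre-surgery narcotic use is not marked at baseline in the table of events, and Appendix A lists only 0-72 hours post-op for overall narcotic data, so it would have to be retrieved from the hospital record.

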AE Stop Date: ____ / ____ / ____

AE Resolved: Yes No

AE Type: AE SAE

AE Description: _____

Is this event listed on the consent form? Yes No

Severity:	 Mild- Grade1	Relationship:	 Not Related
	 Moderate – Grade 2		 Possibly Related
	 Severe – Grade 3		 Probably Related
	 Life Threatening – Grade 4		 Related
	 Fatal - Grade 5		

Actions Taken:	 None	Clinical Outcomes:	 Death
	 Medication Administered		 Recovered Baseline
	 Additional Treatment		 Recovered w sequelae
	 Withdrawn from Study		 Symptoms Continue
	 Other		

Burn Sub-I Signature: _____

Investigator Signature: _____

Patient Initials: _____ **Page 1 of 1**

Patient ID: ____-____

All medication data information will be collected and entered into an excel spreadsheet.

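### Adverse events other than donor-site infection have no planned comparison by arm, and the adverse event form has no clock times, which weakens attribution of early events

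*Combined protocol and SAP*

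**What the plan says.** **Method.** Section 6, Study Design item h: "Any adverse event occurring with the patient will be analyzed on a case-by-case basis". The next sentence names the one adverse outcome that is compared: "Wound infection rates of the donor sites at post op day 14-21 +/- 5 days will be compared between the two groups". The Analysis Plan covers pain ratings and narcotic or hydromorphone use, and plans no adverse event summary by arm. The Safety Monitoring Plan asks for events to be documented and investigated. It also schedules a second safety analysis after 10 more evaluable patients, without defining its content.

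**Expected effects.** Section 7 lists for lidocaine: "Side effects of Lidocaine include: Nausea, drowsiness, mental/mood changes, ringing in the ears, dizziness, vision changes, tremors, numbness, headache and backache". For surgery under general anaesthesia the same section says: "These include reactions to the anesthesia, medications, nausea, pain, problems breathing, excessive bleeding, and infection". Study Design item c adds opioids for all patients. For those who need more than 2 mg of hydromorphone in recovery, "subsequent pain will be treated with Ketamine IV (10mg every 15 minutes up to 50mg total) and 1-2mg of IV midazolam".

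**Timing.** The Background reports of an earlier donor-site study: "In this study the levels peaked between 30 and 60 minutes". It adds that lidocaine was still detectable at 6 hours.

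**Form.** The Adverse Events form in Appendix C has start and stop dates, a description, severity, actions taken and a four-level relationship field (for example "Possibly Related"). It has no time of day. Other Appendix C pages do record clock times: soak on and off, spray, extubation, post-operative admission, pain scores and both lidocaine draws.

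**The concern.** Nausea or drowsiness in the recovery room after sevoflurane, fentanyl and hydromorphone says little about its own cause. A blinded reader taking such events one at a time will tend to put them down to the background drugs in both arms. A modest excess on lidocaine could then pass unseen, although the trial has a concurrent randomised control that could display it. The reverse also matters: if lidocaine spares opioids, a reduction in opioid side effects is a benefit that case review cannot show.

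The missing clock time is a second, separate defect. It bears on judging single events, not on comparing the arms.

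At stake is the protocol's statement that adverse events are unlikely. The evidence it gives from the first 15 patients is lidocaine levels, not event rates by arm.

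**Working it through.** **1. Which safety outcomes are compared between arms?**

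| Outcome | Stated handling | By arm? |
|---|---|---|
| Donor-site infection | rates compared (Study Design h) | yes |
| Time to TheraBond removal | analysed (Study Design i) | not spelled out |
| Lidocaine level | per patient and per graft area (Study Design g) | no |
| All other adverse events | case by case (Study Design h) | no |
| Second safety analysis | content undefined (Safety Monitoring Plan f) | not stated |

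**2. Do the listed effects overlap?** In section 7 itself, nausea and breathing trouble appear under both lidocaine and surgery or anaesthesia. Drowsiness, dizziness and mental or mood changes are listed for lidocaine, in patients who also receive opioids and sometimes ketamine and midazolam. The overlap is not complete: ringing in the ears, tremors, numbness and seizures are more distinctive.

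**3. How finely can an event be timed?** The cited peak window is 30 minutes wide (30 to 60 minutes), and detection runs to at least 6 hours. A date places an event only to within 24 hours. From the form alone, an event near the peak and one ten hours later can carry the same date.

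**4. The plan's own sample size.** The Analysis Plan gives d = 0.8, alpha 0.05, power 0.8 and 25 per group.

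n per arm = 2 × (1.96 + 0.8416)² / 0.8² = 2 × 7.849 / 0.64 = 24.5, so 25.

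The figure reproduces for a two-sided test (power 0.807 by normal approximation, 0.791 by exact noncentral t). It was set for pain scores; the plan gives no figure for adverse events.

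**5. Precision of a by-arm table.** The documents give no event rates, so a common rate p in both arms is assumed. Half-width of the 95% CI for the risk difference (Wald) = 1.96 × √(2p(1−p)/25):

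| Assumed p | Calculation | Half-width |
|---|---|---|
| 10% | 1.96 × √0.0072 | 16.6 points |
| 20% | 1.96 × √0.0128 | 22.2 points |
| 30% | 1.96 × √0.0168 | 25.4 points |
| 40% | 1.96 × √0.0192 | 27.2 points |

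For an event never seen in one arm, the one-sided 95% upper bound is 1 − 0.05^(1/25) = 11.3%.

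**6. Would a test be useful?** Two-sided Fisher power at 25 per arm, by enumeration under assumed rates:

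- 10% v 20%: 0.09
- 20% v 40%: 0.23
- 30% v 50%: 0.23
- 30% v 60%: 0.51
- 5% v 40%: 0.82

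Only a very large difference would be detected reliably, so the table should describe and not test.

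**The case against.** **Attribution is already supported.** The form carries a relationship judgement, a severity grade and free text. The investigator is blinded, exposure times are on the surgical page, and lidocaine is measured at 60 minutes and 6 hours. This stands against any claim that events cannot be attributed. It does not supply an onset time to set beside those clock times. The levels also help only partly: there are two draws, and a reader who sees a measurable level may infer the arm.

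**Safety is compared and monitored.** A reader might infer that the arms are never compared on safety, or that nothing but oximetry ("Patients will be monitored with pulse oximetry overnight per standard of care") watches the patient after surgery. The documents support neither reading. Infection is compared by arm, the Study Table of Events schedules adverse event assessment at every stage from baseline to follow-up, and the dressing site is checked daily. What remains is that no by-arm summary is planned for the other events.

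**A missing clock time does not block a comparison of arms.** Correct. In a blinded randomised trial, counts by date are enough for that, which is why the two defects are kept apart here.

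**The timing problem is narrower than it looks.** Soak and spray are applied under general anaesthesia, so self-reported symptoms cannot begin before emergence. This shortens the period in question but does not remove it: the hours after emergence are when opioid and rescue doses are given.

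**The trial is too small.** True for testing, as step 6 shows. It is no reason to omit counts and intervals.

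**Conclusion.** The point holds in two separate parts. First, apart from donor-site infection, no comparison of adverse events by arm is planned, so the randomised control is not used for non-specific symptoms. Second, the Adverse Events form has dates without clock times, which weakens but does not prevent attribution of early events.

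The second safety analysis might include a table by arm, since nothing excludes it, but nothing requires it either.

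A by-arm table would be imprecise: half-widths of about 17 to 27 points, assuming 25 evaluable patients per arm and common rates of 10% to 40%. It would also estimate a net effect. Ketamine and midazolam depend on hydromorphone need, and lidocaine is meant to reduce that need. A direct lidocaine effect could therefore be offset by less opioid or rescue use. The change is worth making because it is cheap, not because it will settle the safety question.

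**What to change.** - **Analysis.** Replace the case-by-case sentence in Study Design item h, and add to the Analysis Plan: all adverse events will be tabulated by arm as number and percentage of patients with the event, with the risk difference and 95% CI (a method suited to small counts, such as Newcombe's). No significance test or claim will be made. Serious events will also be reviewed individually.
- **Interpretation.** State that the difference is a net effect that includes any change in opioid or rescue use, and give the expected precision (about 17 to 27 points at 25 per arm under assumed rates of 10% to 40%).
- **Form.** Add clock times to the start and stop fields for events on the day of surgery and the next day.

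The cost is one table and two form fields, with no new visit, and the estimates will be imprecise. A prompted symptom checklist on the pain pages is not recommended: asking about numbness beside the donor-site pain score could hint at allocation to the staff who record that score.
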